5.2.4.1 Pulse and blood pressure

Pulse (beats/minute, radial artery, during 30 seconds) will be measured before blood pressure and in a lying or sitting position after 5 minutes of rest. Thereafter, systolic and diastolic blood pressure (mmHg) will be measured using the same cuff, appropriate for arm circumference, and in the same position, throughout the study.

5.2.4.2 Body temperature

Body temperature (Celcius) will be collected at timepoints indicated in [Table 1](#) and according to standard procedures at the clinics.

5.3 Pharmacokinetics

5.3.1 Collection of samples

Blood samples for determination of AZD9567 in plasma will be taken at the times presented in the study plan [Table 1](#).

Blood samples for determination of prednisolone in plasma will also be taken at the times presented in the study plan [Table 1](#).

Samples will be collected, labelled stored and shipped as detailed in the Laboratory Manual.

5.3.2 Determination of drug concentration

Samples for determination of drug concentration in plasma will be analysed by Covance Laboratory Services on behalf of AstraZeneca, using an appropriate bioanalytical method. Full details of the analytical method used will be described in a separate bioanalytical report.

5.3.3 Storage and destruction of pharmacokinetic samples

Pharmacokinetic (PK) samples will be disposed of after the Bioanalytical Report finalization or six months after issuance of the draft Bioanalytical Report (whichever is earlier), unless requested for future analyses.

Pharmacokinetic samples may be disposed of or destroyed and anonymised by pooling. Additional analyses may be conducted on the anonymised, pooled pharmacokinetic samples to further evaluate and validate the analytical method. Any results from such analyses may be reported separately from the Clinical Study Report (CSR).

Incurred sample reproducibility analysis, if any, will be performed alongside the bioanalysis of the test samples. The results from the evaluation will not be reported in the CSR but separately in a Bioanalytical Report.

5.4 Pharmacodynamics

5.4.1 Collection of samples

The pharmacodynamics (PD) of oral AZD9567 will be assessed by effects on CRP levels as part of the primary endpoint DAS28-CRP. CRP is collected as part of the lab screen at time points indicated in [Table 1](#). ESR is also collected as an exploratory biomarker and is also part of the lab screen at time points indicated in [Table 1](#). In addition, there will be samples collected for exploratory biomarkers for future exploratory research, see Section [5.6](#).

5.5 Genetics

5.5.1 Collection of optional genetic samples

The subject's consent to participate in the genetic research components of the study is optional.

The blood sample for genetic research will be obtained from the subjects after or at Visit 2, ie after randomisation. Although DNA variants are stable parameter, early sample collection is preferred to avoid introducing bias through excluding subjects who may withdraw due to an adverse event (AE), such subjects would be important to include in any genetic analysis. If for any reason the sample is not drawn at Visit 2, it may be taken at any visit until the last study visit. Only one sample should be collected per subject for genetics during the study.

Samples will be collected, labelled, stored and shipped as detailed in the Laboratory Manual.

5.5.2 Storage and destruction of genetic samples

The processes adopted for the coding and storage of samples for genetic analysis are important to maintain subject confidentiality. Samples will be stored for a maximum of 15 years or as per local regulations from the date of the Last Subject's Last Visit, after which they will be destroyed. DNA is a finite resource that may be used up during analyses. The results of any possible future analyses will not be reported in the CSR, but separately in a scientific report or publication.

No personal details identifying the individual will be available to AstraZeneca or designated organizations working with the DNA

5.6 Biomarker analysis

The subject's consent to the use of donated biological samples is mandatory.

CC1

5.6.1 Storage, re-use and destruction of biological samples

Samples will be stored for a maximum of 15 years from the date of the Last Subject's Last Visit, after which they will be destroyed. CC1

5.6.2 Labelling and shipment of biological samples

The Principal Investigator ensures that samples are labelled and shipped in accordance with the Laboratory Manual.

5.6.3 Chain of custody of biological samples

A full chain of custody is maintained for all samples throughout their lifecycle.

The Principal Investigator at each centre keeps full traceability of collected biological samples from the subjects while in storage at the centre until shipment or disposal (where appropriate) and keeps documentation of receipt of arrival.

The sample receiver keeps full traceability of the samples while in storage and during use until used or disposed of or until further shipment and keeps documentation of receipt of arrival.

AstraZeneca keeps oversight of the entire life cycle through internal procedures, monitoring of study sites and auditing of external laboratory providers.

Samples retained for further use are registered in the AstraZeneca Biobank during the entire life cycle.

5.6.4 Withdrawal of Informed Consent for donated biological samples

If a subject withdraws consent to the use of donated biological samples, the samples will be disposed of/destroyed, and the action documented. If samples are already analysed, AstraZeneca is not obliged to destroy the results of this research.

As collection of the biological samples is an integral part of the study, then the subject is withdrawn from further study participation.

The Principal Investigator:

- Ensures subjects' withdrawal of informed consent to the use of donated samples is notified immediately to AstraZeneca
- Ensures that biological samples from that subject, if stored at the study site, are immediately identified, disposed of /destroyed, and the action documented
- Ensures the organization(s) holding the samples is/are informed about the withdrawn consent immediately and that samples are disposed of/destroyed, the action documented and the signed document returned to the study site
- Ensures that the subject and AstraZeneca are informed about the sample disposal.

AstraZeneca ensures the organizations holding the samples is/are informed about the withdrawn consent immediately and that samples are disposed of/destroyed and the action documented and returned to the study site.

6. SAFETY REPORTING AND MEDICAL MANAGEMENT

The Principal Investigator is responsible for ensuring that all staff involved in the study are familiar with the content of this section.

6.1 Definition of adverse events

An adverse event is the development of any untoward medical occurrence in a subject or clinical study subject administered a medicinal product and which does not necessarily have a causal relationship with this treatment. An AE can therefore be any unfavourable and unintended sign (e.g. an abnormal laboratory finding), symptom (for example nausea, chest pain), or disease temporally associated with the use of a medicinal product, whether or not considered related to the medicinal product.

The term AE is used to include both serious and non-serious AEs and can include a deterioration of a pre-existing medical occurrence. An AE may occur at any time, including run-in or washout periods, even if no study treatment has been administered.

6.2 Definitions of serious adverse event

A serious adverse event is an AE occurring during any study phase (i.e., run-in, treatment, washout, follow-up), that fulfils one or more of the following criteria:

- Results in death
- Is immediately life-threatening
- Requires in-subject hospitalisation or prolongation of existing hospitalisation
- Results in persistent or significant disability or incapacity.
- Is a congenital abnormality or birth defect
- Is an important medical event that may jeopardise the subject or may require medical intervention to prevent one of the outcomes listed above.

For further guidance on the definition of a SAE, see [Appendix A](#) to the Clinical Study Protocol.

6.3 Recording of adverse events

6.3.1 Time period for collection of adverse events

Adverse Events will be collected from randomisation, Visit 2 throughout the treatment period and including the follow-up period Visit 6.

SAEs will be recorded from the time of informed consent.

6.3.2 Follow-up of unresolved adverse events

Any AEs that are unresolved at study Visit 6 are followed up by the Investigator for as long as medically indicated, but without further recording in the CRF. AstraZeneca retains the right to request additional information for any subject with ongoing AE(s)/SAE(s) at the end of the study, if judged necessary.

6.3.3 Variables

The following variables will be collect for each AE;

- AE (verbatim)
- The date and time when the AE started and stopped
- Maximum intensity,
- Intensity rating scale:
- mild (awareness of sign or symptom, but easily tolerated)

- moderate (discomfort sufficient to cause interference with normal activities)
- severe (incapacitating, with inability to perform normal activities)
- Whether the AE is serious or not
- Investigator causality rating against the Investigational Product (yes or no)
- Action taken with regard to investigational product
- AE caused subject's withdrawal from study (yes or no)
- Outcome.

In addition, the following variables will be collected for SAEs:

- Date AE met criteria for serious AE
- Date Investigator became aware of serious AE
- AE is serious due to
- Date of hospitalization
- Date of discharge
- Probable cause of death
- Date of death
- Autopsy performed
- Causality assessment in relation to Study procedure(s)
- Causality assessment to other medication,
- Description of AE.

It is important to distinguish between serious and severe AEs. Severity is a measure of intensity whereas seriousness is defined by the criteria in Section 6.2. An AE of severe intensity need not necessarily be considered serious. For example, nausea that persists for several hours may be considered severe nausea, but not a SAE unless it meets the criteria shown in Section 6.2. On the other hand, a stroke that results in only a limited degree of disability may be considered a mild stroke but would be a SAE when it satisfies the criteria shown in Section 6.2.

6.3.4 Causality collection

The Investigator will assess causal relationship between Investigational Product and each Adverse Event, and answer 'yes' or 'no' to the question 'Do you consider that there is a reasonable possibility that the event may have been caused by the investigational product?'

For SAEs causal relationship will also be assessed for other medication and study procedures and additional study drug. Note that for SAEs that could be associated with any study procedure the causal relationship is implied as 'yes'.

A guide to the interpretation of the causality question is found in [Appendix A](#) to the Clinical Study Protocol.

6.3.5 Adverse events based on signs and symptoms

All AEs spontaneously reported by the subject or reported in response to the open question from the study site staff: *'Have you/the child had any health problems since the previous visit?'*, or revealed by observation will be collected and recorded in the CRF. When collecting AEs, the recording of diagnoses is preferred (when possible) to recording a list of signs and symptoms. However, if a diagnosis is known and there are other signs or symptoms that are not generally part of the diagnosis, the diagnosis and each sign or symptom will be recorded separately.

6.3.6 Adverse events based on examinations and tests

The results from the Clinical Study Protocol mandated laboratory tests and vital signs will be summarised in the CSR. Deterioration as compared to baseline in protocol-mandated laboratory values, vital signs should therefore only be reported as AEs if they fulfil any of the SAE criteria or are the reason for discontinuation of treatment with the investigational product.

If deterioration in a laboratory value/vital sign is associated with clinical signs and symptoms, the sign or symptom will be reported as an AE and the associated laboratory result/vital sign will be considered as additional information. Wherever possible the reporting Investigator uses the clinical, rather than the laboratory term (e.g., anaemia versus low haemoglobin value). In the absence of clinical signs or symptoms, clinically relevant deteriorations in non-mandated parameters should be reported as AE(s).

Deterioration of a laboratory value, which is unequivocally due to disease progression, should not be reported as an AE/SAE.

Any new or aggravated clinically relevant abnormal medical finding at a physical examination as compared with the baseline assessment will be reported as an AE

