6.3.8 Disease under Study (DUS)

Symptoms of DUS are those which might be expected to occur as a direct result of active RA. Events, which are unequivocally due to disease under study should not be reported as an AE

during the study unless they meet SAE criteria or lead to discontinuation of the investigational product.

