6.4 Reporting of serious adverse events

All SAEs have to be reported, whether or not considered causally related to the investigational product, or to the study procedure(s). All SAEs will be recorded in the CRF.

If any SAE occurs in the course of the study, then Investigators or other site personnel inform the appropriate AstraZeneca representatives within one day i.e., immediately but **no later than 24 hours** of when he or she becomes aware of it.

The designated AstraZeneca representative works with the Investigator to ensure that all the necessary information is provided to the AstraZeneca Patient Safety data entry site **within 1 calendar day** of initial receipt for fatal and life threatening events **and within 5 calendar days** of initial receipt for all other SAEs.

For fatal or life-threatening adverse events where important or relevant information is missing, active follow-up is undertaken immediately. Investigators or other site personnel inform AstraZeneca representatives of any follow-up information on a previously reported SAE within one calendar day i.e., immediately but **no later than 24 hours** of when he or she becomes aware of it.

Once the Investigators or other site personnel indicate an AE is serious in the WBDC system, an automated email alert is sent to the designated AstraZeneca representative.

If the WBDC system is not available, then the Investigator or other study site staff reports a SAE to the appropriate AstraZeneca representative by telephone.

The AstraZeneca representative will advise the Investigator/study site staff how to proceed.

The reference document for definition of expectedness/listedness is the IB for the AstraZeneca drug and the EU Summary of Product Characteristics (SPC) for the active comparator product.

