4.8.6.1 Adverse events

Summary tables will include TEAEs only, unless otherwise specified. That is, pre- and post-treatment AEs will not be included in the summary tables of AEs. Any AE after discontinuation of study treatment and pre-treatment AEs will be flagged in the data listings as post-treatment AEs and pre-treatment AEs, respectively.

Pre-treatment AEs are defined as AEs with start date before the first dose of study treatment.

TEAEs are defined as AEs with start date and time \geq the first dose of study treatment and \leq the last dose of study treatment + 14 days.

Post-treatment AEs are defined as AEs with start date $>$ the last dose of study treatment + 14 days.

If an AE has a missing onset date then unless the stop date of the AE indicates otherwise, this will be considered treatment emergent. Similarly, if an AE has a partial onset date, then unless the partial onset date or the stop date indicates otherwise, this will be considered a TEAE. In cases where the AE start time is missing but the AE start date is the same as the first dose of study treatment, then that AE will be considered a TEAE.

An overall summary table will be produced showing the number and percentage of subjects with at least 1 AE for each of the following categories:

- Any AE.
- Any AE with an outcome = death.
- Any AE with an outcome = death, causally related to study treatment.
- Any SAE (including events with outcome = death).
- Any AE leading to discontinuation of study treatment.
- Any AE causally related to study treatment.
- Any AE with intensity = severe.

AEs will be summarised by MedDRA SOC and MedDRA PT. For each SOC/PT, the number and percentage of subjects reporting at least one occurrence will be presented i.e., for a subject, multiple occurrences of an AE will be only counted once.

Summaries will also be done on AEs with most common frequency ($\geq 5\%$), non-serious AEs occurring in $\geq 5\%$ subjects, causally related to study treatment, outcome of death, serious AEs, SAEs causally related to study treatment, leading to discontinuation of the study treatment, and leading to discontinuation of study treatment, causally related to study treatment. Number and percentage of subjects with AEs by PT and relationship will also be provided.

A summary of the number and percentage of AEs by SOC and PT will be presented along with a separate summary of the number and percentage of SAEs by SOC and PT.

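### Protocol 6.3.6 says a laboratory deterioration due to disease progression is not reported even as an SAE, contradicting 6.3.8 and, for serious events, 6.4

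*Protocol*

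**What the plan says.** Five provisions bear on the point.

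- **Protocol 6.1** lets a laboratory result be an adverse event: "An AE can therefore be any unfavourable and unintended sign (e.g. an abnormal laboratory finding"). It also counts worsening of a pre-existing condition.
- **Protocol 6.3.6, first paragraph**, says deterioration in mandated laboratory values and vital signs should "only be reported as AEs if they fulfil any of the SAE criteria or are the reason for discontinuation of treatment" with study drug.
- **Protocol 6.3.6, later in the same section**, says: "Deterioration of a laboratory value, which is unequivocally due to disease progression, should not be reported as an AE/SAE". No exception follows.
- **Protocol 6.3.8** covers the disease under study. It begins: "Events, which are unequivocally due to disease under study should not be reported as an AE", and continues: "during the study unless they meet SAE criteria or lead to discontinuation of the investigational product".
- **Protocol 6.4** says: "All SAEs have to be reported, whether or not considered causally related to the investigational product, or to the study procedure(s"). Sites must inform the sponsor within 24 hours of becoming aware.

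In the analysis, SAP 4.8.6.1 counts patients with any SAE and, separately, "Any AE leading to discontinuation of study treatment". Both counts depend on the event having been entered as an AE.

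**The concern.** The sentence in 6.3.6 names SAEs explicitly, so a site cannot assume that it gives way to 6.4. It is also narrower than the first paragraph of its own section and comes after it, so a site could reasonably treat it as the specific rule that overrides the general one. Section 6.3.8 shows how the protocol handles disease-related events elsewhere: they are excluded, with two exceptions. Section 6.3.6 has the exclusion without the exceptions.

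The setting makes this worth correcting. Section 1.1 describes the study as the first in patients, and Section 4.2 says 5 days is the longest clinical exposure so far, so most of the 14-day course is new. Under 6.4 the automated alert is sent only once a site marks an AE as serious. An event that the site has been told not to report triggers no alert.

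**Working it through.** No arithmetic applies to the contradiction itself. The check is to take one kind of event, a deterioration in a mandated laboratory value judged unequivocally due to RA progression, and read each provision against it.

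| Case | 6.3.6, first paragraph | 6.3.6, progression sentence | 6.3.8 | 6.4 |
|---|---|---|---|---|
| (a) Meets an SAE criterion | Reportable | Do not report | Exception applies: not excluded | Report |
| (b) Not serious, but the reason study drug was stopped | Reportable | Do not report | Exception applies: not excluded | Silent |
| (c) Neither | Do not report | Do not report | Do not report | Silent |

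**Case (a)** is a direct contradiction. The progression sentence opposes 6.4, 6.3.8 and the first paragraph of 6.3.6.

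**Case (b)** contradicts 6.3.8. It is also at odds with the first paragraph of 6.3.6, although less cleanly: that paragraph is worded as a limit on reporting (report only if), so the later sentence could be read as a further limit. Section 6.4 does not cover this case.

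**Case (c)** shows no conflict. The progression sentence does its intended job there, which is to keep ordinary fluctuation of disease markers out of the AE data.

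**Can the event occur here?** Protocol Table 2 lists CRP and ESR among the safety laboratory variables. Section 5.1.1 uses them as the acute-phase terms of the two DAS28 versions. A mandated safety test can therefore worsen because RA worsens.

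**What survives if the site follows the progression sentence?**

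- Clinical signs or symptoms that accompany the laboratory change are still AEs (6.3.6, second paragraph).
- Laboratory values are still summarised by visit, with shift tables and with line plots that include CRP and ESR (SAP 4.8.6.3).
- Reasons for stopping treatment are documented (Protocol 3.11), and summarised and listed (SAP 4.8.1 and 4.8.5).

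**What does not survive?** The SAE report to the sponsor in case (a), and in either case the entry in the corresponding AE tables of SAP 4.8.6.1.

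**Weight of one event.** SAP 1.3 gives both 20 planned and 10 agreed per group. One omitted patient changes a group's rate by 1/20 = 5 or 1/10 = 10 percentage points. This would be true of any single event and says nothing about how often this one occurs.

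**The case against.** The strongest reply is that the conflict is real on paper but has little room to operate.

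- **Serious events.** SAE criteria are mostly clinical outcomes such as death or hospitalisation. A laboratory change that reaches one would usually come with signs or symptoms, which 6.3.6 has reported as AEs and which fall under 6.4 if serious. What is left is an isolated laboratory value, unequivocally due to RA, that still meets a criterion.
- **Discontinuation.** Table 1 schedules post-baseline laboratory tests during treatment at Visits 4 and 5 only, and Visit 5 is the end of treatment. One scheduled sample, plus any ad hoc test, could prompt an early stop. Section 3.9 names no laboratory threshold for stopping.
- **Other text.** Section 6.2 refers sites to Appendix A for SAE guidance. That appendix is not in the text reviewed here, so whether it clarifies the point could not be checked.

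The first two arguments stand as limits on frequency. None of the three changes what the sentence tells a site to do.

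A reader might also infer more than the documents support:

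- **That the omission would favour the less effective arm.** No document gives progression or event rates by arm, both arms are active, and Protocol 8.2 states an aim of equivalence.
- **That a range of lost events can be stated.** No frequency is given, so any such range would be invented.
- **That haemoglobin, platelets and leukocytes are affected in the same way.** They are in the panel, but the documents tie only CRP and ESR to RA activity.
- **That such patients would disappear from the report.** They would still appear in the laboratory summaries and, if they stopped treatment, in disposition.

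**Conclusion.** The contradiction holds on the current text. It is complete for a serious laboratory deterioration attributed to disease progression. For a non-serious one that leads to discontinuation it is a conflict with 6.3.8, with a weaker tension against the first paragraph of 6.3.6.

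Its effect is confined to safety reporting and AE classification: a possible missing 24-hour SAE report, and possible missing entries in the SAP's SAE and discontinuation-AE tables. The efficacy analysis is not affected. The number of patients cannot be estimated from the documents and is probably small. The conclusion assumes only that a site applies the sentence as written and that Appendix A does not override it. It is a wording error that should be corrected, because sites should not hold opposite written instructions on whether an SAE is reported.

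**What to change.** Reconcile the sentence in Protocol 6.3.6 with 6.3.8 and 6.4. Remove SAE from the exclusion, and add the two exceptions that 6.3.8 already contains. Wording to this effect would do:

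*A laboratory deterioration that is unequivocally due to disease progression is not recorded as an AE, except where it fulfils an SAE criterion or is why the investigational product was stopped (see 6.3.8 and 6.4).*

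Keep the term disease progression. Replacing it with disease under study would change, and arguably widen, the exclusion for non-serious laboratory values.

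Send sites a short note on the change. The cost is one protocol sentence and that note, with no new data collection and no change to the SAP analyses. The downside is a possible small rise in reported SAEs and discontinuation AEs.
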